5.3.3 Non-hematologic Toxicities

- The management of general AEs not otherwise specified in the following sections should be as per **Table 5**.
- Dose modifications for nausea, vomiting, and diarrhea will be made only if they are refractory to treatment. The time a given drug is held should not exceed 21 days.

Table 4. General Recommendations for Dose Modification and Management of Non-Hematological Toxicities

Observation	Management
-------------	------------

Grade 1 non-hematologic AE	Maintain dose level.
Any grade 2 non-hematologic AE related to study drug(s) lasting >7 days despite maximal intervention	Hold study drug(s)** for up to 21 days until toxicity resolves to ≤ grade 1. Treatment with ¹⁷⁷ Lu-DOTA ⁰ -Tyr ³ -Octreotate may be restarted one dose level lower.
Any ≥ grade 3 non-hematologic*	Hold study drug(s)** for up to 21 days until toxicity resolves to ≤ grade 1 or baseline. Treatment with ¹⁷⁷ Lu-DOTA ⁰ -Tyr ³ -Octreotate may be restarted one dose level lower.
Grade 3 or 4 non-hematologic AE related to drugs* that does not resolve to grade 1 or less within 21 days despite maximum supportive care after treating patient at the lowest reduced DL.	Remove patient from study regimen.

* Excluding 1) Grade 3 fatigue/asthenia < 2 weeks in duration, or grade 3 asymptomatic electrolytes imbalance with optimal and continuing repletion that downgrades to grade 1 or better within 7 days after onset of the event; 2) Grade 3 asymptomatic increase in gamma glutamyl transferase (GGT).

** For patients on combination therapy, if the observed AE is specifically attributed to only 1 of the drugs, that drug may be held while the patient continues to receive the drug not associated with the observed AE. The time a given drug is held should not exceed 21 days.

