5.0 TREATMENT PLAN

5.1 Treatment Dosage and Administration

5.1.1 Phase I

5.1.1.1 Dose Limiting Toxicity (DLT)

A DLT is defined as any toxicity not attributable to the disease or disease-related processes under investigation, which occurs from the first dose of study treatment (Day 1, Cycle 1) up to the last day of the cycle (Day 57). To be considered as DLT, it must be related to the study drugs (attributions: possible, probable, and definite) while fulfilling one of the following criteria as per the NCI Common Toxicity Criteria for Adverse Events (CTCAE) version 4.03:

- Toxicity grade 2 for platelets and any other grade 3 or 4 toxicity, excluding
 - Grade 3 diarrhea, nausea, or vomiting if it can be controlled with supportive therapy
 - Grade 3 endocrinopathy that is managed with or without systemic corticosteroid therapy and/or hormone replacement therapy and the patient is asymptomatic.
- Persistent (>21 days) non-hematologic grade 2 adverse events despite optimal medical management and treatment delay > 21 days
- Any other toxicity:
 - if worse than baseline value, documented, clinically relevant and/or unacceptable, and is judged to be a DLT by the investigators
 - if results in a protocol defined stopping criteria
 - if results in disruption of dosing schedule

Patients experiencing DLT will be monitored weekly until toxicity stabilization, and then every two weeks until normalization.

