5.3.1 General Recommendations for Evaluation of Toxicities and Dose Delays/Modifications

Any patient who receives treatment on this protocol will be evaluable for toxicity. Toxicity will be assessed according to the NCI Common Toxicity Criteria for Adverse Events (CTCAE), version 4.03. Dose delays or dose modifications should be made according to the system showing the greatest degree of toxicity. Once the patient has a dose reduction due to toxicity, the dose will not

be re-escalated. Dose delays and dose modifications will be made using the following recommendations. At the discretion of the investigator, the study drugs may be held or dose modified independently if the observed AE is attributed to only one of the study drugs, while the patient continued to receive the drug not associated with the observed AE. For example, if the patient develops immune-related adverse events, nivolumab may be held following guidelines in section 5.3.5 while the patient continues to receive $^{177}\text{Lu-DOTA}^0\text{-Tyr}^3\text{-Octreotate}$. If the patient develops hematologic adverse events that are frequently associated with $^{177}\text{Lu-DOTA}^0\text{-Tyr}^3\text{-Octreotate}$, but rarely associated with nivolumab (e.g. thrombocytopenia), $^{177}\text{Lu-DOTA}^0\text{-Tyr}^3\text{-Octreotate}$ may be held while the patient continues on nivolumab. If the observed toxicity is attributable to both drugs, both drugs will be held.

Dose modifications for $^{177}\text{Lu-DOTA}^0\text{-Tyr}^3\text{-Octreotate}$ are permitted according to the table below.

Dose Level (DL)	$^{177}\text{Lu-DOTA}^0\text{-Tyr}^3\text{-Octreotate}$ (IV)
Level 1	3.7 GBq (100 mCi) every 8 weeks
Level 2	7.4 GBq (200 mCi) every 8 weeks

No dose modifications are allowed for nivolumab.

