Grade 2 AE	Hold nivolumab until grade 2 resolution to \leq grade 1. If toxicity worsens, then treat as grade 3 or grade 4. If toxicity improves to baseline, then consider restarting nivolumab.	Systemic corticosteroids should be considered for a persistent low-grade event or for a more severe event. Patients on IV steroids may be switched to an equivalent dose of oral corticosteroids (e.g. prednisone) at start of tapering or earlier, once sustained clinical improvement is observed. Lower bioavailability of oral corticosteroids should be taken into account when switching to the equivalent dose of oral corticosteroids.
Grade 3 AE**	Depending on the individual toxicity, may permanently discontinue nivolumab*	More potent immunosuppressive agents should be considered for events not responding to systemic steroids (e.g., infliximab, mycophenolate, etc.). Discontinuation of study drug is not mandated for Grade 3 / Grade 4 inflammatory reactions attributed to local tumor response (e.g., inflammatory reaction at sites of metastatic disease, lymph nodes etc.). Continuation of study drug in this situation should be based upon a benefit/risk analysis for that patient.

Grade 4 AE**	Permanently discontinue nivolumab.	
--------------	------------------------------------	--

* In addition to the criteria for permanent discontinuation of study drug/regimen based on CTC grade/severity, permanently discontinue study drug/study regimen for the following conditions: 1) Inability to reduce corticosteroid to a dose of ≤ 10 mg of prednisone per day (or equivalent) within 12 weeks after last dose of study drug/regimen, 2) Recurrence of a previously experienced Grade 3 treatment-related AE following resumption of dosing.

** For Grade 3 and above asymptomatic amylase or lipase levels, hold study drug/regimen and if complete work up shows no evidence of pancreatitis, may continue or resume study drug/regimen

Abbreviations: ADL=activities of daily living, ALT=alanine aminotransferase, AST=aspartate aminotransferase, irAE=immune-related adverse event, IV=intravenous, LLN=lower limit of normal, MRI=magnetic resonance imaging, NSAIDs=nonsteroidal anti-inflammatory drugs, T4=thyroxine, TSH=thyroid-stimulating hormone, ULN=upper limit of normal, IVIG=intravenous immunoglobulins, CPK=creatine phosphokinase.

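### Table 4 holds study drug for related grade 2 fatigue lasting 8 to 13 days but exempts grade 3 fatigue of the same length

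*Combined protocol and SAP*

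**What the plan says.** Three parts of the protocol bear on this.

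**Table 4, section 5.3.3.** The grade 2 row is triggered by "Any grade 2 non-hematologic AE related to study drug(s) lasting >7 days despite maximal intervention". The action is to hold the study drug(s) "for up to 21 days until toxicity resolves to ≤ grade 1", after which 177Lu "may be restarted one dose level lower". This row has no asterisk. The next row, "Any ≥ grade 3 non-hematologic", carries an asterisk and prescribes a similar hold with the same restart option. The removal row for unresolved grade 3 or 4 events is also asterisked. The footnote begins "Excluding 1) Grade 3 fatigue/asthenia < 2 weeks in duration, or grade 3 asymptomatic electrolytes imbalance with optimal and continuing repletion"; the electrolyte item must also improve to grade 1 or better within 7 days of onset.

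**Dose levels, section 5.3.1.** Level 2 is "7.4 GBq (200 mCi) every 8 weeks" and level 1 is 3.7 GBq on the same schedule. Nothing lower is listed. A dose reduced for toxicity is not raised again. Nivolumab is not dose-modified.

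**DLT definition, section 5.1.1.1.** For phase I, cycle 1, related events only, the main criterion is "Toxicity grade 2 for platelets and any other grade 3 or 4 toxicity, excluding". The exclusions that follow cover controllable grade 3 diarrhea, nausea or vomiting, and managed asymptomatic grade 3 endocrinopathy. Fatigue and electrolytes are not among them.

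**The concern.** A graded management table should not become more lenient as the event becomes more severe. For one event, fatigue or asthenia, Table 4 does so over a band of durations, because an exemption written for grade 3 was not carried to the grade 2 row.

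Two sites following the table could act differently. One would apply the grade 2 row literally, hold treatment and perhaps reduce 177Lu for good. Another would judge it unreasonable to hold grade 2 when grade 3 is exempt. Hold and reduction data, and delivered 177Lu activity, would then depend partly on how each site read a footnote. The table is not limited to one phase, so this can arise in phase I and in the phase II treatment arm.

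**Working it through.** The plan states no figure to reproduce. The check is to apply the two rows to the same event and vary its duration.

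**Inputs.** Grade 2 trigger: related, more than 7 days, despite maximal intervention (Table 4, no asterisk). Grade 3 trigger: any, except fatigue or asthenia of less than 2 weeks (Table 4 and footnote). Dose levels: 7.4 and 3.7 GBq (section 5.3.1). Number of 177Lu administrations: 4 (section 9.1.1).

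**Rule by duration.** Let d be whole days of related fatigue at the stated grade, treated maximally.

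- Grade 2: hold if d > 7.
- Grade 3: exempt if d < 14, so hold if d ≥ 14.

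| Duration d | Grade 2 | Grade 3 |
|---|---|---|
| up to 7 days | no hold | exempt |
| 8 to 13 days | hold; 177Lu may restart lower | exempt |
| 14 days or more | hold; 177Lu may restart lower | hold; 177Lu may restart lower |

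The order is inverted when d > 7 and d < 14, that is on days 8 to 13: 13 − 8 + 1 = 6 whole days. Outside that band Table 4 treats the two grades alike on holding.

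**Reading of the footnote.** The 7-day recovery condition reads naturally as part of the electrolyte item, since fatigue has its own 2-week limit. The electrolyte item shows no inversion: grade 3 is exempt only if it falls to grade 1 or better within 7 days, and the grade 2 row starts only after 7 days. The fatigue item overlaps the grade 2 trigger because its limit is 14 days. I also take the exemption to apply while an episode is running. If it applied only once the episode had ended, it could not prevent a hold.

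**Size of the optional reduction.** One level down from level 2 is 3.7 / 7.4 = 0.50. Four full doses are 4 × 7.4 = 29.6 GBq. If the option is used from dose 2, the total is 7.4 + 3 × 3.7 = 18.5 GBq, or 18.5 / 29.6 = 62.5%. If it is used only at dose 4, the total is 3 × 7.4 + 3.7 = 25.9 GBq, or 87.5%. From level 1 there is no listed lower level, so no reduction is available.

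**DLT list beside the hold list.** Related grade 3 fatigue of 10 days in cycle 1 meets the grade 3 or 4 criterion in section 5.1.1.1 but needs no hold under Table 4. So does a rapidly corrected asymptomatic grade 3 electrolyte disturbance. Grade 2 fatigue of 10 days does not meet the persistent grade 2 criterion, which needs more than 21 days. If it is held, it might still meet the separate item on disruption of the dosing schedule.

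**The case against.** The best reply is that the reach is small. The band is six days wide. The grade 2 hold needs relatedness and failure of maximal intervention, the reduction is permissive, and section 5.3.1 lets the investigator hold a drug to which an event is attributed. No one is obliged to dose through grade 3 fatigue. 177Lu is given every 8 weeks and may slip by a week (section 5.2.1), so many such episodes fall between doses. All of this stands, and it limits the consequence. It does not remove the inverted default. Nivolumab is given every 2 weeks, so six days is a larger share of its interval, and the grade 2 row does not say whether the lower 177Lu restart applies when no dose was missed.

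Several stronger readings are tempting but not supported:

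- **That the DLT definition contradicts Table 4 and so undermines the recommended phase II dose.** Section 5.1.1.1 decides escalation in phase I, cycle 1; section 5.3 decides dosing of the individual patient. A DLT list broader than the hold list is a defensible conservative choice. Putting a figure on its effect on escalation would need event rates that the documents do not give, and the escalation table words the highest level differently (at most 2 of 6).
- **That asymptomatic amylase or lipase elevation is a DLT although dosing simply continues.** Table 6 says "For Grade 3 and above asymptomatic amylase or lipase levels, hold study drug/regimen and if complete work up shows no evidence of pancreatitis", so the hold comes first and any resumption depends on the work-up.
- **That GGT shows the same inversion.** The footnote does exempt asymptomatic grade 3 GGT. But GGT is not listed in the biochemical profile (section 6.1) or the study calendar (Appendix D), and section 8.1.1 counts a laboratory value as an adverse event only under listed conditions. An untreated, asymptomatic grade 2 rise would ordinarily not reach the grade 2 row.

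**Conclusion.** Table 4 contradicts itself on fatigue and asthenia. For related episodes lasting more than 7 and less than 14 days despite maximal intervention, grade 2 requires a hold of up to 21 days with an optional lower 177Lu restart, while grade 3 requires no hold. This follows from where the asterisk is placed and needs no assumed rates. It rests on reading the 2-week limit as the only limit on the fatigue exemption, and on that exemption applying during the episode.

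The practical size is modest: six days of duration, one event type, and a 50% cut in later 177Lu doses only from level 2 and only if the option is taken. How often it would occur cannot be estimated from the documents. The difference between the DLT list and the hold list is a possible design choice that should be stated, not an error.

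**What to change.** Reconcile the grade 2 row of Table 4 with the asterisked footnote so that, for the same event and duration, a higher grade never gets a weaker action than a lower grade. The sponsor decides which rule stands; this review takes no view on it.

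In the same edit, add a sentence to section 5.1.1.1 saying whether related cycle 1 events that Table 4 exempts from a hold (short grade 3 fatigue, rapidly corrected asymptomatic grade 3 electrolyte disturbance) are meant to count as DLTs. If they are, say that this is intended although no hold is required.

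The cost is protocol wording. The downside is that some events will change hold status, so if patients are already on study the date of the change should be recorded to keep hold and dose-reduction summaries interpretable.

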5.3.4 Management of Infusion-Related Reactions

Table 5. Dose Modifications and Management of Infusion-Related Reactions

Observation	Management
Grade 1 or 2 AE	The infusion rate of study drug(s) may be decreased by 50% or temporarily interrupted until resolution of the event. Acetaminophen and/or antihistamines may be administered per institutional standard at the discretion of the investigator. Consider premedication prior to subsequent doses.
Grade 3 or 4 AE	Discontinue study drug(s). Manage severe infusion-related reactions (e.g., IM epinephrine, followed by IV diphenhydramine and ranitidine, and IV glucocorticoid).

5.3.5 Management of Immune-Related Toxicities

Treatment of immune-related adverse events (irAEs) should follow guidelines set forth in the following tables. Also, please refer to Appendix B for details.

Table 6. Dose Modification and Management of irAEs

Gastrointestinal irAEs (e.g. diarrhea, colitis)		
Observation	Management	Follow-up
Grade 1 AE	Continue nivolumab therapy. Consider symptomatic treatment (e.g. loperamide, hydration, electrolyte replacement).	Close monitoring for worsening symptoms. Educate patient to report worsening immediately. If worsens: Treat as Grade 2 or 3/4
Grade 2 AE	Delay nivolumab therapy. Symptomatic treatment.	If improves to Grade 1: Resume nivolumab therapy. If no improvement within 5-7 days or recur: Consider starting IV methylprednisolone 0.5-1.0 mg/kg/day or oral equivalent. Once improving, taper steroids over ≥ 1 month and consider prophylactic antimicrobials for opportunistic infections, and consider resuming nivolumab. If the event is not responsive within 3-5 days or worsens despite steroid: Treat as Grade 3/4.
Grade 3 to 4 AE	Discontinue nivolumab therapy. 1.0 to 2.0 mg/kg/day methylprednisolone IV or equivalent. Consider urgent GI consult and imaging and/or colonoscopy as appropriate.	Once improving, taper steroids over ≥ 1 month and consider prophylactic antimicrobials for opportunistic infections. If still no improvement within 3-5 days or recurs after improvement despite steroid: consider adding further immunosuppressives (e.g. infliximab at 5mg/kg once every 2 weeks if no contraindication). Caution: Consider GI

		consult to rule out bowel perforation and refer to infliximab label for general guidance before using infliximab. Infliximab should not be used in cases of perforation or sepsis.
--	--	--

Dermatological irAEs		
Observation	Management	Follow-up
Grade 1-2 AE	Symptomatic therapy (e.g. oral antihistamines, topical steroids). Continue nivolumab therapy.	If persists > 1-2 weeks or recurs: Consider delaying nivolumab. Consider skin biopsy. Consider 0.5-1.0 mg/kg/day methylprednisolone IV or oral equivalent. Once improving, taper steroids over \geq 1 month, consider prophylactic antimicrobials for opportunistic infections, and resume nivolumab. If worsens: Treat as Grade 3-4.
Grade 3-4 AE	Delay or discontinue nivolumab therapy. 1.0 to 2.0 mg/kg/day methylprednisolone IV or equivalent. Consider dermatology consult and/or skin biopsy.	If improves to Grade 1: taper steroids over \geq 1 month and consider prophylactic antimicrobials for opportunistic infections and consider resuming nivolumab.

Pulmonary irAEs		
Observation	Management	Follow-up
Grade 1 AE	Consider delay of nivolumab therapy. Monitor for symptoms at least every 2-3 days.	Re-image at least every 3 weeks. If worsens: Treat as Grade 2 or Grade 3-4.

	Consider Pulmonary and Infectious Disease consults.	
Grade 2 AE	
Delay nivolumab therapy.
 
Consider Pulmonary and Infectious Disease consults.
 
Monitor symptoms daily, consider hospitalization.
 
1.0 mg/kg/day methyl-prednisolone IV or oral equivalent.
 
Consider bronchoscopy, lung biopsy.
	
Re-image every 1-3 days.
 
If improves: When symptoms return to near baseline, taper steroids over ≥ 1 month, resume nivolumab therapy, and consider prophylactic antimicrobials.
 
If not improving after 2 weeks or worsening: Treat as Grade 3 to 4.

Grade 3 or 4 AE	
Discontinue nivolumab therapy.
 
Hospitalize.
 
Pulmonary and Infectious Disease consults.
 
2 to 4 mg/kg/day methylprednisolone IV or IV equivalent.
 
Add prophylactic microbials for opportunistic infections.
 
Consider bronchoscopy, lung biopsy.
	
If improves to baseline: Taper steroids over at least 6 weeks.
 
If not improving within 48 hours or worsening: Add additional immunosuppression (e.g. infliximab, cyclosporine, tacrolimus, cyclophosphamide, intravenous immunoglobulin, or mycophenolate mofetil).

Hepatic irAEs		
Observation	Management	Follow-up
Grade 1 AE	Continue nivolumab therapy.	Continue liver function monitoring. If worsens: Treat as Grade 2 or 3-4.
Grade 2 AE	
Delay nivolumab therapy.
 
Regular and frequent checking (e.g. every 3 days) of LFTs until elevations of these are improving or resolved.
	If returns to baseline: Resume routine monitoring, resume nivolumab therapy.

		If elevations persist > 5-7 days or worsen: 0.5 to 1 mg/kg/day methylprednisolone or oral equivalent and when LFT returns to Grade 1 or baseline, taper steroids over \geq 1 month, consider prophylactic antimicrobials for opportunistic infections, and resume nivolumab therapy.
Grade 3 to 4 AE	
Discontinue nivolumab therapy*
 
Regular and frequent checking of LFTs (e.g. every 1-2 days) until elevations of these are improving or resolved.
 
1.0 to 2.0 mg/kg/day methylprednisolone IV or IV equivalent**
 
Add prophylactic antimicrobials for opportunistic infections.
 
Consult gastroenterologist.
	
If returns to Grade 2 or better: Taper steroids over \geq 1 month.
 
If does not improve in > 3 to 5 days, worsens or rebounds: Add mycophenolate mofetil 1 gram (g) twice daily. If no response within an additional 3 to 5 days, consider other immunosuppressants per local guidelines.

*Nivolumab therapy may be delayed rather than discontinued if AST/ALT \leq 8 x ULN and Total bilirubin \leq 5 x ULN.

**The recommended starting dose for grade 4 hepatitis is 2 mg/kg/day methylprednisolone IV.

Endocrine irAEs		
Endocrine Disorder	Management	Follow-up
Asymptomatic TSH elevation	
Continue nivolumab therapy.
 
If TSH < 0.5 x LLN, or TSH > 2 x ULN, or consistently out of range in 2 subsequent measurements: include free T4 at subsequent cycles as clinically indicated; consider endocrinology consult.
	
Symptomatic endocrinopathy	
Evaluate endocrine function.
 
Consider pituitary scan.
	
If improves (with or without hormone replacement): Taper steroids over \geq 1 month and consider prophylactic antimicrobials for opportunistic infections.
 
Resume nivolumab therapy.

	
Symptomatic with abnormal lab / pituitary scan: Delay nivolumab therapy. 1 to 2 mg/kg/day methylprednisolone IV or by mouth equivalent. Initiate appropriate hormone therapy.
 
No abnormal lab / pituitary MRI scan but symptoms persist: Repeat labs in 1 to 3 weeks / MRI in 1 month
	
Subjects with adrenal insufficiency may need to continue steroids with mineralocorticoid component.

Suspicion of adrenal crisis (e.g. severe dehydration, hypotension, shock out of proportion to current illness)
	
Delay or discontinue nivolumab therapy.
 
Rule out sepsis.
 
Stress dose of IV steroids with mineralocorticoid activity.
 
IV fluids.
 
Consult endocrinologist.
 
If adrenal crisis ruled out, then treat as above for symptomatic endocrinopathy.
	

Renal irAEs		
Observation	Management	Follow-up
Grade 1 AE	
Continue nivolumab therapy.
 
Monitor creatinine weekly.
	
If returns to baseline: resume routine creatinine monitoring per protocol.
 
If worsens: Treat as Grade 2 or 3/4.

Grade 2-3 AE	
Delay nivolumab therapy.
 
Regular and frequent checking of Creatinine (e.g. every 2-3 days) until Creatinine elevation is improving or resolved.
 
0.5 to 1 mg/kg/day methylprednisolone IV or oral equivalent.
 
Consider renal biopsy with nephrology consult.
	
If returns to grade 1: Taper steroids over \geq 1 month, consider prophylactic antimicrobials for opportunistic infections, and resume nivolumab therapy and routine creatinine monitoring per protocol.
 
If elevations persist > 7 days or worsen: Treat as Grade 4.

Grade 4 AE	
Discontinue nivolumab therapy.
 
Regular and frequent checking of Creatinine until Creatinine elevation is improving or resolved.
 
1 to 2 mg/kg/day methylprednisolone iv or iv equivalent.
 
Consult nephrologist.
 
Consider renal biopsy.
	
If returns to Grade 1: Taper steroids over ≥ 1 month, consider prophylactic antimicrobials for opportunistic infections.

------------	--	---

Neurological irAEs		
Observation	Management	Follow-up
Grade 1 AE	
Continue nivolumab therapy.
	
Continue to monitor the patient.
 
If worsens: Treat as Grade 2 or 3/4.

Grade 2 AE	
Delay nivolumab therapy.
 
Treat symptoms per local guidelines.
 
Consider 0.5 to 1 mg/kg/day methylprednisolone iv or oral equivalent.
	
If improves to baseline or grade 1: Resume nivolumab therapy per protocol when improved to baseline.
 
If worsens: Treat as Grade 3-4.

Grade 3-4 AE	
Discontinue nivolumab therapy.
 
Obtain neurology consult.
 
Treat symptoms per local guidelines.
 
1 to 2 mg/kg/day methylprednisolone IV or equivalent.
 
Add prophylactic antibiotics for opportunistic infections.
	
If improves to grade 2: Taper steroids over ≥ 1 month.
 
If worsens or atypical presentation: consider IVIG or other immunosuppressive therapies per local guidelines.

Other irAEs		
Observation	Dose Modifications	Toxicity management
Grade 1 AE	Continue nivolumab therapy. Consider appropriate symptomatic treatment.	Subjects should be evaluated to identify any alternative etiology. Symptomatic and/or topical therapy should be considered for low grade events.
Grade 2 AE	Hold nivolumab until grade 2 resolution to \leq grade 1. If toxicity worsens, then treat as grade 3 or grade 4. If toxicity improves to baseline, then consider restarting nivolumab.	Systemic corticosteroids should be considered for a persistent low-grade event or for a more severe event. Patients on IV steroids may be switched to an equivalent dose of oral corticosteroids (e.g. prednisone) at start of tapering or earlier, once sustained clinical improvement is observed. Lower bioavailability of oral corticosteroids should be taken into account when switching to the equivalent dose of oral corticosteroids.
Grade 3 AE**	Depending on the individual toxicity, may permanently discontinue nivolumab*	More potent immunosuppressive agents should be considered for events not responding to systemic steroids (e.g., infliximab, mycophenolate, etc.). Discontinuation of study drug is not mandated for Grade 3 / Grade 4 inflammatory reactions attributed to local tumor response (e.g., inflammatory reaction at sites of metastatic disease, lymph nodes etc.). Continuation of study drug in this situation should be based upon a benefit/risk analysis for that patient.

Grade 4 AE**	Permanently discontinue nivolumab.	
--------------	------------------------------------	--

* In addition to the criteria for permanent discontinuation of study drug/regimen based on CTC grade/severity, permanently discontinue study drug/study regimen for the following conditions: 1) Inability to reduce corticosteroid to a dose of ≤ 10 mg of prednisone per day (or equivalent) within 12 weeks after last dose of study drug/regimen, 2) Recurrence of a previously experienced Grade 3 treatment-related AE following resumption of dosing.

** For Grade 3 and above asymptomatic amylase or lipase levels, hold study drug/regimen and if complete work up shows no evidence of pancreatitis, may continue or resume study drug/regimen

Abbreviations: ADL=activities of daily living, ALT=alanine aminotransferase, AST=aspartate aminotransferase, irAE=immune-related adverse event, IV=intravenous, LLN=lower limit of normal, MRI=magnetic resonance imaging, NSAIDs=nonsteroidal anti-inflammatory drugs, T4=thyroxine, TSH=thyroid-stimulating hormone, ULN=upper limit of normal, IVIG=intravenous immunoglobulins, CPK=creatine phosphokinase.

